These will consist of infants, children and adolescents of any race or gender who have had samples sent to the Mass Spectrometry Laboratory for assessment for defects in bile acid metabolism because of the presence of cholestasis, or unexplained fat and fat-soluble vitamin malabsorption. They will have been identified by urine bile acid analysis by fast atom bombardment ionization mass spectrometry as having defects in bile acid conjugation based upon characteristic mass spectra. Prior to our planned studies, patients will have undergone a thorough evaluation to define the etiology of their cholestasis or fat-soluble vitamin deficiency. Conventional screening studies (urine culture and clinitest, a1-antitrypsin phenotype, STORCH titers, thyroid function tests, liver ultrasound, liver "function" tests and percutaneous liver biopsy) will have been performed. Patients with other organ dysfunction will not be excluded. Only patients identified with inborn errors of bile acid synthesis caused by defective bile acid conjugation will be candidates for entry to this study. The possible effect of radiation exposure during this study on an unborn baby is unknown. Because of this possibility, all females that may be able to become pregnant will have a urine pregnancy test done before starting the study, and before any x-ray exposure. It is anticipated that such defects are rare; however, there are 3 candidates for study at this time and we anticipate identification of one or more new patients each year that would be candidates for study on this protocol.

Study Protocol:

Once a patient is identified by [name] as having a potential defect in bile acid conjugation, the attending physician will be contacted by [name] to discuss enrollment of the patient in the study. He will explain the study to the parents/patients, and if they are willing, the subject will be brought to the Children's Hospital Clinical Research Center.

On admission, the patient will have studies to assess liver function (bilirubin, ALT, AST, GGT, alkaline phosphatase, cholesterol, albumin, prothrombin time), partial thromboplastin time, serum tocopherol, serum retinol, serum 25-OH vitamin D and PIVKA-II. A full nutritional evaluation will be performed including anthropometrics (height, weight. weight/height and OFC). Serum will be obtained to perform a complete bile acid analysis by gas-liquid chromatography and urine will be obtained for LSIMS and GC-MS analysis (total blood for study purposes <10 cc).

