
Primary bile acid pool-sizes will be measured to determine whether the hypothesized contraction of pools might play a role in the pathogenesis of cholestasis in these subjects. $[2,2,4,4-^{2}H_{4}]$ Cholic acid (15 mg) and $[11,12-^{2}H_{2}]$ chenodeoxycholic acid (15 mg) will be given by mouth at or soon after 2100 h on the evening of Day 1 on the GCRC. Nothing will be taken by mouth after midnight but a glass of water may be taken up to 6 hours before the procedure to collect bile on day 2. After an overnight fast, a nasoduodenal tube will be passed with the aid of fluoroscopy. Bile will be collected after gallbladder contraction with the octapeptide CCK. After bile collection, the tube will be removed. A blood sample will be taken for DNA sequencing and detection of mutations in the two genes encoding the bile acid conjugation enzymes. On Day 3, after four hour fast 100 IU/kg liquid emulsified dl-alpha-tocopherol will be given orally with collection of blood (1.0 cc/sample) at 0, +4, +8, +12, +18, +24, +48 hours after ingestion (32,33). On Day 4, after a 4 hour fast 1,000 IU/kg Vitamin D₃ will be ingested in 3-5 oz of formula and blood (1.0 cc/sample) collected at 0, 6, 12, and 24 hours as previously described (34,35). Formula may be resumed 1 hour after the test dose of vitamin D. After completion of the last serum sample, the patient will begin therapy with 15 mg/kg glycocholic acid (IND #50,046) by mouth and discharged from the GCRC the morning of Day 5 after receiving at least 2 doses of the bile acid treatment. Liver function tests (as described above), and serum and urine for bile acid analysis by GC-MS and LSIMS. Three to twelve months after initiation of therapy, the patient will return to the GCRC for evaluation and measurement of liver function tests, nutritional assessment, measurement of the fasting primary bile acid pool-sizes, measurement of vitamin E and 25-OH vitamin D absorption. If bile acid therapy is considered to be successful based upon clinical findings, bile acids will be continued indefinitely with periodic follow-up by our group, or by the referring physician. Samples of urine will be collected every 3-12 months to assess compliance and response to therapy. Liver function tests will be performed at the discretion of the attending physician as the standard of care. It is anticipated that they will be collected at least once/year. This follow-up would be considered standard care for patients affected with cholestatic disorders of this nature.

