Venipuncture may be accompanied by pain and bruising at the site. Cumulative blood losses at each of the two hospitalizations on the GCRC will be 21 ccs which is approximately 5% of the blood volume of even the smallest enrolled subject (6 kg x 70 x 0.05 = 21 cc). The passage of a nasoduodenal tube may result in mild-to-moderate discomfort. The nasopharynx will be anesthetized with a topical anesthetic to minimize discomfort. Fluoroscopy required for passage of the tube results in modest radiation exposure. Fluoroscopy will be performed on 2 occasions. This will produce an average exposure of 225 mrem for each intubation and 450 mrem for the two exposures. The scientific value of the information obtained from this study as it relates to our basic understanding of cholestasis and specifically as it related to the pathogenesis of disease in the study subjects makes this radiation exposure warranted.

There are no recognized hazards associated with the use of small quantities of stable isotopes as proposed in the current protocol. There may be some nausea, abdominal cramping with the use of CCK-octapeptide for collection of bile. Although diarrhea might be a potential complication of bile acid therapy, no significant problem to date has been found in the infants and children treated with UDCA or cholic acid. Treatment of more than 100 cholestatic children with ursodeoxycholic acid has not led to any measurable deterioration in hepatic function. In fact, administration of ursodeoxycholic acid uniformly leads to reductions in serum concentrations of bilirubin, transaminases, and cholesterol in most cholestatic conditions, while primary bile acid therapy has led to normalization of liver function in all patients studied with inborn errors in bile acid synthesis. Similarly, although diarrhea might be a potential complication of bile acid therapy, no significant problem has been found in the infants and children treated with cholic or ursodeoxycholic acids. It is not anticipated that there will be a different safety profile when conjugates of cholic acid are used for treatment.

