Risk/Benefit Assessment. The above risks are considered to be more than minimal to these patients; however, the subjects may directly benefit from the proposed therapy with conjugated bile acids. In addition, it is possible that patients with these conditions as a class may benefit by our improved understanding of the pathogenesis of this disease process and the optimization of the therapeutic approach.

Data and Safety Monitoring Plan

This study represents more than minimal risk to subjects with potential benefit. This is a treatment intervention similar to one that has not been associated with any significant adverse events associated with the administration of the drug since the initiation of treatment studies in 1994. Currently, we review any adverse events for causality and they are kept in tabular form in the investigator's password protected database. For any serious adverse events or unanticipated adverse events, the investigator would report

deaths to the IRB, GCRC and FDA within 2 days and other SAEs and unanticipated AEs would be reported to the IRB, GCRC and FDA within 10 working days of the investigator's knowledge of their occurrence. Any SAEs that are considered related or probably related to the use of glycocholic acid will result in halting of enrollment of subjects and review by an Independent Medical Monitor. [name]. will serve as Lead Independent Medical Monitor. He will be responsible for the timely evaluation of any AE's, SAE's and unanticipated AE's for causality and relationship to the study drug at least every six months.

VII. Estimated Time to Complete Study.

More than 5-10 years.

VIII. Funding

Funding is provided from the NIH supported Cholestatic Liver Consortium (CLiC) Grant # 5U54DK078377-04

IX. Payment for Studies

All costs related to visit 2 will be assigned to the grant from CLiC. There will be no incentives provided for participation in this study. There are no funds available to cover transportation costs to the study site for study related visits.

X. Methods to be used in Procuring Informed Consent

A verbal explanation will be given to the parent/guardian by phone prior to coming to CCHMC for Visit 1. Written consent will be obtained at screening before enrollment in the study at CCHMC. The informed consent form is attached.

XI. Attending Physician Approval

Not applicable

References

- 1. Balistreri WF: Neonatal cholestasis. Seminars in Liver Disease 7:61-66,1987.

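### Does the 5% blood-loss figure need changing because no minimum weight of 6 kg is set?

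*Combined protocol and SAP*

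**What the plan says.** The risk section (V/VI, Potential Risks and Discomforts) states: "Cumulative blood losses at each of the two hospitalizations on the GCRC will be 21 ccs which is approximately 5% of the blood volume". It applies that share to "even the smallest enrolled subject (6 kg x 70 x 0.05 = 21 cc"). No unit is printed for the 70; cc per kg of body weight is implied.

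The blood draws are set out in section IV, Study Protocol:

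- Admission: "total blood for study purposes <10 cc".
- Tocopherol absorption test, Day 3: "with collection of blood (1.0 cc/sample) at 0, +4, +8, +12, +18, +24, +48 hours after ingestion".
- Vitamin D absorption test, Day 4: the dose "will be ingested in 3-5 oz of formula and blood (1.0 cc/sample) collected at 0, 6, 12, and 24 hours".
- A blood sample for DNA sequencing, listed after the Day 2 bile collection, with no volume given.

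On who may enter, section IV, Study Subjects, says: "These will consist of infants, children and adolescents of any race or gender". Entry depends on a diagnosis of defective bile acid conjugation, and no lower age or weight is given. The same section says "there are 3 candidates for study at this time and we anticipate identification of one or more new patients each year", and section VII gives the time to complete the study as "More than 5-10 years".

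**The concern.** A percentage said to hold even for the smallest subject reads as an upper bound. It is one only if nobody weighs materially less than 6 kg, and in the text available that weight appears nowhere except in this calculation. The draws are fixed volumes, so the share of blood volume rises as weight falls. With only three candidates known and recruitment expected to run for years, most subjects' weights may not have been known when the sentence was written.

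What would be at stake is the accuracy of a risk description given to the institutional review board. For an infant lighter than 6 kg, whom the eligibility text does not exclude, the true share would exceed the stated one.

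**Working it through.** **Inputs from the document.** 21 cc per hospitalization, 6 kg, 70 cc/kg and 5% (section V/VI); under 10 cc at admission, 7 samples of 1.0 cc and 4 samples of 1.0 cc (section IV, Study Protocol).

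**Assumptions, not in the document.** Weights below 6 kg; blood volumes of 80 and 85 cc/kg; any volume for the DNA sample.

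**1. The plan's own figure.** 6 × 70 × 0.05 = 21.0 cc. In reverse, 21 / (6 × 70) = 21 / 420 = 5.0%. It reproduces exactly.

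**2. Agreement with the draws.** (<10) + 7 × 1.0 + 4 × 1.0 = less than 21 cc. The stated total matches the upper end of the schedule. A small DNA sample fits if the admission draw leaves room for it. If instead it came on top of a full 21 cc, then at 6 kg an assumed 1 cc would give 22 / 420 = 5.24% and an assumed 3 cc would give 24 / 420 = 5.71%.

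**3. Share at lower weights.** Share = 21 / (weight × cc/kg).

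| Weight | 70 cc/kg (plan) | 80 cc/kg (assumed) | 85 cc/kg (assumed) |
|---|---|---|---|
| 5 kg | 21/350 = 6.00% | 21/400 = 5.25% | 21/425 = 4.94% |
| 4 kg | 21/280 = 7.50% | 21/320 = 6.56% | 21/340 = 6.18% |
| 3 kg | 21/210 = 10.00% | 21/240 = 8.75% | 21/255 = 8.24% |

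**4. How far the rounding stretches.** If anything below 5.5% counts as about 5%, the limiting weight is 21 / (cc/kg × 0.055): 5.45 kg at 70, 4.77 kg at 80 and 4.49 kg at 85. At 4 kg and below the statement fails on all three blood volumes.

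**5. What depends on the figure.** The Data Analysis text uses paired t-tests, repeated-measures ANOVA and areas under the curve. The number of subjects follows from how many patients are identified. None of this takes blood volume as an input. No limit on blood loss is stated that a higher percentage could breach. The Risk/Benefit Assessment already places the study above minimal risk.

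**The case for a change.** The strongest case for acting is that young infants are plainly within scope. The abstract opens with neonatal cholestasis, the first hypothesis concerns early life, and the vitamin D dose is given in formula. The study also examines effects on growth, so low weight for age cannot be dismissed. A review board would read the sentence as a ceiling, and at 3 kg and the plan's own 70 cc/kg the share would be 10.0%, twice the stated figure. Rewording would cost one sentence.

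Part of this stands: the wording promises more than the eligibility text guarantees, and rounding does not rescue it at 4 kg or below. The rest is weaker.

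- Nothing in the text contradicts 6 kg. Silence on weight in the eligibility section does not conflict with an assumption printed in full elsewhere.
- The sentence may describe the candidates known when it was written. The expected new patients make that reading less natural but do not exclude it.
- Part of the background on the conjugation defect was not available for this review. Patient weights might appear there, so it cannot be said that 6 kg lacks support.
- Patients will have completed a diagnostic work-up, including liver biopsy, before entry. That sets no weight floor, but neither does anything show 3 to 4 kg to be a realistic case.
- The percentages at lower weights are close to upper bounds, because the itemised draws sum to less than 21 cc unless the DNA sample uses up the difference.

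**Conclusion.** The concern is right that 6 kg is an assumption, but it shows no error and no inconsistency in the plan. The arithmetic is correct, the total agrees with the schedule, and the inputs are printed where the result is used. The size is modest and hypothetical: at 70 cc/kg, about 6.0% instead of 5.0% at 5 kg and 7.5% at 4 kg, if such a child is enrolled. How often that would happen cannot be judged from the document.

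Rewording the sentence would alter no endpoint, analysis, sample or conclusion. The only response that would alter conduct is an entry restriction by weight. That is a clinical decision and would trade a tidier risk statement against access for infants with a very rare defect; the statistical review has no ground to ask for it. Readers can take the 5% as applying at 6 kg and rescale it for a lighter child. The plan can stand as it is.

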2. Treatment of affected infants/children with conjugated bile acids will lead to resolution of liver disease, if present, and improvements in fat and fat-soluble vitamin absorption

In order to address the above interrelated hypotheses we will perform the following:

1. We will determine the extent of alteration in biliary bile acid composition and measure the primary bile acid pool sizes by the administration of stable-isotope labeled primary bile acids, and correlate these with the concentration of unconjugated bile acids and with markers of liver dysfunction.

2. We will administer the conjugate of the primary bile acid, glycocholic acid, to patients with disorders in bile acid conjugation, monitor its metabolic fate and determine the effect of bile acid therapy on biliary bile acid composition and it ability to correct the clinical manifestation of fat and fat-soluble vitamin malabsorption.

3. Where liver dysfunction is present at diagnosis and liver biopsies have been obtained during the evaluation of the patient, a single follow-up liver biopsy will be performed after treatment to assess the effect of therapy on liver histology and ultrastructural pathology.

II. Significance of the study in relation to human health

Liver disease in infancy has many definable causes, including known infections, anatomic defects, well delineated metabolic errors, and inherited or acquired defects in hepatobiliary structure and function. However, "idiopathic" neonatal hepatitis syndromes make up by far the largest proportion (35-40%) of cases of liver disease in neonates and children [1]. The frequent pattern of intrafamilial recurrence for many of these cases suggested to us a genetic basis, and this was subsequently substantiated by our description some years ago of two inborn errors in bile acid synthesis presenting as progressive cholestatic conditions. More recently we have described three additional unique defects in bile acid synthesis.

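### A death or serious hepatic event not considered related or probably related to glycocholic acid has no monitor-review deadline shorter than six months

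*Combined protocol and SAP*

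**What the plan says.** The Data and Safety Monitoring Plan has three layers.

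- **Reporting.** Deaths go to the IRB, GCRC and FDA within 2 days. Other SAEs and unanticipated AEs go to the same bodies within 10 working days of the investigator's knowledge. Neither depends on attribution.
- **Event trigger.** "Any SAEs that are considered related or probably related to the use of glycocholic acid will result in halting of enrollment of subjects", and the sentence goes on to require review by an Independent Medical Monitor. No number of days is given for that review.
- **Ongoing evaluation.** The monitor is responsible for the "timely evaluation of any AE's, SAE's and unanticipated AE's for causality and relationship to the study drug at least every six months". This covers every event, whatever its label.

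On who judges causality, the section says "Currently, we review any adverse events for causality". It does not say whose judgement fires the trigger, and it gives no causality scale.

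For context, Study Subjects (Section IV) says samples are referred "because of the presence of cholestasis, or unexplained fat and fat-soluble vitamin malabsorption". Section V/VI states "It is not anticipated that there will be a different safety profile when conjugates of cholic acid are used for treatment". Data Analysis (Section IV) compares subjects before and after treatment and with previously published results; there is no concurrent control arm. Study Drug (Section IV) has drug dispensed three months at a time.

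**The concern.** The attribution label decides whether anything happens automatically, and in this study the label can be hard to assign. In a child who entered for vitamin malabsorption without liver disease, a serious liver event would stand out. In a child who entered with cholestasis, the same event could be the disease or the drug, and there is no control group to show the background rate. Anything judged less than probable, such as an event a clinician would call possible, falls outside the trigger.

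For such an event the monitor could comply with the plan and still give a first evaluation nearly six months later. Meanwhile the other children stay on drug and new children may start. The plan's halt also covers enrolment only. Even when it fires, nothing asks the monitor whether children already on treatment should go on receiving the drug. What is at stake is the timing of the monitor's opinion for a small group of treated children.

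**Working it through.** **Step 1. What each event sets in motion under the Data and Safety Monitoring Plan.**

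| SAE | Report to IRB, GCRC, FDA | Automatic enrolment halt | Monitor review | Opinion on continued supply |
|---|---|---|---|---|
| Considered related or probably related | 2 days (death) or 10 working days | Yes | Triggered; no number of days | Not required |
| Any other death or SAE | Same | No | Timely, at least six-monthly | Not required |

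The rows differ only in the halt and the triggered review.

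**Step 2. Information available for attribution.** It is more than a baseline and one repeat:

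- a full work-up before entry, including percutaneous liver biopsy (Study Subjects), and an admission liver panel (Study Protocol);
- outpatient follow-up laboratories before the repeat stay (Abstract). Study Protocol has an incomplete sentence listing liver tests and bile acid samples between discharge and the return visit, with no timing. Data Analysis plans a repeated-measures analysis of serial liver tests;
- the 3-12 month repeat evaluation, then urine every 3-12 months;
- for some subjects, a biopsy: "Where liver dysfunction is present at diagnosis and liver biopsies have been obtained during the evaluation of the patient, a single follow-up liver biopsy" (Section I).

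In long-term follow-up, "Liver function tests will be performed at the discretion of the attending physician as the standard of care", anticipated at least once a year. These data help, but without a control arm they need not separate disease progression from drug effect in a cholestatic child.

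**Step 3. Days gained by a fixed limit.** Let T be the interval between monitor evaluations, with the event falling evenly within it and known at once. Take 10 working days as 14 calendar days.

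- Longest wait now: T. Mean wait now: T/2.
- Mean wait with the limit: 14 − 14²/(2T).
- Mean gain: T/2 − (14 − 14²/(2T)). Largest gain: T − 14.

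| Monitor looks every | T (days) | Mean wait now | Largest gain | Mean gain |
|---|---|---|---|---|
| 6 months (stated limit) | 182.6 | 91.3 | 168.6 | 77.8 |
| 3 months (assumed) | 91.3 | 45.7 | 77.3 | 32.7 |
| 1 month (assumed) | 30.4 | 15.2 | 16.4 | 4.4 |

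First row: 91.3 − (14 − 196/365.25) = 91.3 − 13.5 = 77.8.

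**Step 4. Children to whom the opinion would apply.** Study Subjects says "there are 3 candidates for study at this time and we anticipate identification of one or more new patients each year". Assume all 3 start, r enter per year and none stops, so the number on drug after t years is 3 + r·t. With r = 1 this is 4 after year 1 and 8 after year 5; with an assumed r = 2 it is 5 and 13. Leaving out the child with the event gives 3 to 12 others. This is an upper count for each r, because therapy continues only if judged successful and while drug is available. A six-month wait spans up to 6/3 = 2 resupplies per child.

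**Step 5. New entry during the wait.** With Poisson entry at rate r per year:

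- Full six months, 1 − exp(−0.5r): 39.3% (r = 1), 63.2% (r = 2).
- Averaged over an even wait, 1 − (1 − exp(−0.5r))/(0.5r): 21.3% (r = 1), 36.8% (r = 2).
- Within 14 days, 1 − exp(−14r/365.25): 3.8% (r = 1), 7.4% (r = 2). In a year when the 3 current candidates also enter: 14.2% (r = 4), 17.4% (r = 5).

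The first two lines give the chance of ordinary enrolment before review, not of avoidable harm. The third shows that an automatic 14-day hold would be close to neutral, since any entrant it shields is also an entrant it delays.

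**The case against.** The strongest reply is that the plan already covers these events. Deaths and SAEs reach three bodies outside the study team quickly, whatever the attribution. The monitor must evaluate all events in a timely way, and six months is an outer bound. This stands in part. A reader might infer that such an event would get no independent look for six months, or that children would continue with no outside opinion at all. The documents do not support that. What remains is narrower: the reporting layer states no opinion or action that must follow, and the monitor's duty has no shorter limit.

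A second reply is that nobody knows who sets the label. A reader might infer that the study team does, and that its expectation of an unchanged safety profile would bias it. The text does not establish either. It is silent on whose judgement counts, and it gives the monitor a causality role. An expectation about safety is not evidence of mislabelling. The silence is itself worth repairing, but the point does not depend on the answer.

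Third, a reader might infer that attribution rests on a baseline panel and a single repeat. Step 2 of the working shows that it does not.

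Finally, the days gained do not measure harm. They depend on a qualifying event, an uncertain or wrong label, and a monitor who would have advised something different. None of these has a rate in the documents. This stands in full.

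**Conclusion.** The point holds in a limited form. The plan ties its enrolment halt and its triggered monitor review to an attribution that can be uncertain in a cholestatic child without a control group, and it leaves six months as the only numeric limit on monitor evaluation of every other death or serious hepatic event. The weakness is possible delay in the monitor's review, together with the lack of any required opinion on continued dosing. It is not an absence of oversight.

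The gain from a fixed limit is at most about 169 days. It averages about 78 days if the monitor looks only six-monthly, falling to about 33 or 4 if the monitor in practice looks quarterly or monthly. These figures assume events spread evenly between looks and recognised at once. The rate of wrong labels, and so the harm avoided, cannot be estimated from the documents. The change is worth making because it is cheap and the subjects are children on open-ended treatment, not because the plan is shown to be unsafe.

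**What to change.** Add one paragraph to the Data and Safety Monitoring Plan:

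- For any death and any serious hepatic event, whatever the attribution, the existing Independent Medical Monitor reviews the case within 10 working days of the investigator's knowledge, the limit the plan already uses for SAE reports.
- A serious hepatic event is an SAE of liver failure, listing for transplant, or admission for new or worsening liver dysfunction.
- The monitor gives a written opinion on new entry and on continued drug supply to treated subjects.
- The automatic halt for related or probably related SAEs stays as it is. Any other hold on entry is left to the monitor.

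It would also help to state whose judgement fires the automatic halt.

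The cost is a few extra short reviews, many of which may conclude that the disease was the cause. If every treated child had one such event, that would be 4 reviews on the year-1 count at one entry per year, and 13 on the year-5 count at an assumed two. No new tests, visits or staff are needed.
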